- 1. Public Purpose: Hemorrhage is the most preventable cause of death in trauma Epidemiologic studies at civilian trauma centers have revealed patients. hemorrhage as responsible for up to 50% of trauma related mortality. But despite improvements in patient transport via EMS, survival in the first hour postinjury has changed little over the past 40 years. Crystalloids remain the mainstay of treatment without a convincing reduction of mortality due to blood loss. Thawed plasma, as a third generation fluid for initial resuscitation, appears logical and promising, but has not been evaluated. While many urban trauma centers can provide various blood products, including thawed plasma, as required in the ED and in the field, the vast majority of rural trauma centers cannot resemble the austere conditions of the military frontline environment. Stage I will allow this study to be generalizable to the most typical scenario in the U.S., i.e., thawed plasma only available in the ED. Moreover, as we have witnessed, natural disasters and acts of terrorisms cause mass casualties that can overwhelm labile blood product resources. A stable plasma preparation that can be stored for longer periods is necessary for these situations. Civilian trauma victims will benefit from longer time for transportation as well as more time for blood banks to prepare and deploy specific blood components. Blood products, especially pRBCs have been associated with increased morbidity and mortality among civilian trauma victims who will likely experience improved outcomes with decreased blood product utilization. In addition, our already depleted blood supplies will benefit from decreased utilization.
- 2. Military Significance: Traumatic blood loss due to combat related injuries is the primary cause of death in field combatants. While significant advances have been made in the prevention and treatment of hemorrhage with the introduction of novel hemostatic dressings and tourniquets, little progress has been made in developing new resuscitation strategies. Primary resuscitation using crystalloids is the current standard of care. Crystalloids only provide a means to temporarily increase intravascular volume to maintain blood pressure and may not be the optimal initial resuscitation fluid in traumatic hemorrhagic shock. The proposed study will elucidate the use of plasma in the pre-hospital setting as an initial resuscitation fluid for traumatic hemorrhage. This project will also be the

gateway study to examine and compare the use of long shelf-life and more logistically accessible resuscitation fluids, such as lyophilized plasma, and, in development, the multifunctional resuscitation fluids. This study will provide an exponential leap forward in the care and development of future therapies for the wounded war fighter in the field. The data generated from this study will provide i. an evaluation of the safety and efficacy of the early use of plasma, ii. information on the mechanism(s) of acute traumatic coagulopathy, and iii. a functional and proteomic baseline to gauge the desired composition of future plasma-based products, such as lyophilized plasma and multifunctional resuscitation fluids. Delaying the requirement of pRBC transfusion will allow longer transport times to combat support units stocked with pRBC in the military theater. In addition, there will be more time to adequately array blood components for transfusion. Decreasing blood products transfusion in the initial postinjury period has implications for decreased need of precious blood products, as well as a decrease in the deleterious effects of blood products in the postinjury period including increased rates of MOF, ARDS, infections and death as well as hospital resources utilization (ICU stay and mechanical ventilation time)

- 3. Waveform Data: Previous research supports the notion that LBNP is a well tested and safe model that can be used to simulate severe hemorrhage approaching cardiovascular collapse in humans. However, data from LBNP experiments have not been directly compared to data collected from bleeding and hemodynamically unstable trauma patients in a hospital setting. If our main hypothesis is proven correct, that the physiologic changes that occur with the application of LBNP mimic those observed in bleeding and hemodynamically unstable trauma patients, then the LBNP model could be used to further explore the human response to severe hemorrhage secondary to trauma. This knowledge would facilitate future research investigating the relationship between continuous physiologic waveform features and central volume loss, and may in the future reveal additional early indicators of hemodynamic instability, cardiovascular collapse and risk of death secondary to traumatic hemorrhage.
- **R.** Changes to the Protocol: Substantive modifications to the research protocol and any modifications that could potentially increase risk to subjects must be submitted to the HRPO for approval prior to implementation. The USAMRMC ORP HRPO defines a substantive modification as a change in Principal Investigator, change or addition of an institution, elimination or alteration of the consent process, change to the study population that has regulatory implications (e.g. adding children, adding active duty population, etc.), significant change in study design (i.e. would prompt additional scientific review), or a change that could potentially increase risks to subjects.
- **S.** Continuing Review and Final Report: A copy of the continuing review report and the re-approval notification by the IRB must be submitted to the HRPO as soon as possible after receipt of approval Please note that the HRPO also conducts random audits at the time of continuing review and additional information and documentation may be requested at that time.

T. The final study report submitted to the IRB, including a copy of any acknowledgement documentation and any supporting documents must be submitted to the HRPO as soon as all documents become available. DOD Funded Research Guidelines: The protocol will not be initiated until written notification of approval of the research project is issued by the HRPO.

Suspensions, clinical holds (voluntary or involuntary), or terminations of this research by the IRB, the institution, the sponsor, or regulatory agencies will be promptly reported to the USAMRMC ORP HRPO. The knowledge of any pending compliance inspection/visit by the Food and Drug Administration (FDA), Office for Human Research Protections, or other government agency concerning this research; the issuance of inspection reports, FDA Form 483, warning letters, or actions taken by any regulatory agencies including legal or medical actions; and any instances of serious or continuing noncompliance with the regulations or requirements must be reported immediately to the HRPO.

References

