PROTOCOL #: 12-1349 VERSION DATE: 12/27/2016

COMIRB Protocol

(Use Protocol Manager on the COMIRB Website)

COLORADO MULTIPLE INSTITUTIONAL REVIEW BOARD [name] [contact] [contact]

Project Title: Control Of Major Bleeding After Trauma (COMBAT): A prospective, randomized comparison of fresh frozen plasma versus standard crystalloid intravenous fluid as initial resuscitation fluid

Principal Investigator: [name].

This study is sponsored by the DOD's Telemedicine & Advanced Technology Research Center (TATRC).

I. Study Main Objective: The main objective of the study is to determine the efficacy of administering plasma (specifically AB-FP24) during field resuscitation compared to current treatment policy or standard of care (SOC) in which normal saline is infused in the pre-ED phase. This Phase 2 trial will provide preliminary evidence to potentially support Phase 3 trials with large study populations.

Study aims:

- 1) To determine if plasma-first resuscitation of severe hemorrhagic shock attenuates the acute coagulopathy of trauma.
- 2) To determine if plasma-first resuscitation of severe hemorrhagic shock improves metabolic recovery.
- 3) To determine if plasma-first resuscitation of severe hemorrhagic shock decreases overall blood product transfusion and reduces the incidence of acute lung injury, multiple organ failure, and mortality. In relation to the efficacy of plasma-first resuscitation, we will assess whether waveform information can help predict activation of the massive transfusion protocol.

II. Background and Significance:

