3	-1.99302	1.99302	0.046259	0.037903	0.050000	0.382549	0.800000
Details whe	en Spending = C)'Brien-Flem	ning, N1 = 68	, N2 =68, P1	= 0.08, P2 =	0.26	
	Lower	Upper	Nominal	Inc	Total	Inc	Total
Look	Bndry	Bndry	Alpha	Alpha	Alpha	Power	Power
1	-3.71030	3.71030	0.000207	0.000207	0.000207	0.018650	0.018650
2	-2.51142	2.51142	0.012025	0.011890	0.012097	0.398801	0.417451
3	-1.99302	1.99302	0.046259	0.037903	0.050000	0.382549	0.800000
Details whe	en Spending = C)'Brien-Flem	ning, N1 = 75	, N2 =75, P1	= 0.09, P2 =	0.26	
	Lower	Upper	Nominal	Inc	Total	Inc	Total
Look	Bndry	Bndry	Alpha	Alpha	Alpha	Power	Power
1	-3.71030	3.71030	0.000207	0.000207	0.000207	0.018650	0.018650
2	-2.51142	2.51142	0.012025	0.011890	0.012097	0.398801	0.417451
3	-1.99302	1.99302	0.046259	0.037903	0.050000	0.382549	0.800000

Addendum Nov 16, 2016

At the second interim analyses, we had enrolled 100 patients (2/3 of the 150 total sample size), of whom 88 (12% attrition rate) patients were eligible for analysis (please, see Interim Analyses report for details). This attrition rate was similar to the lowest anticipated attrition rate (see first table above). Yet we noticed several important differences regarding the assumptions used to estimate the sample size. In brief, the cohort enrolled based on the entry criteria (field systolic blood pressure, SBP<70mmHg or SBP <90mmHg AND heart rate>108bpm) was less severely injured than anticipated (as measured by base deficit, INR and TEG G) and had lower mortality than anticipated.

Variable	Anticipated (sample size/power analyses assumptions)	COMBAT group A	COMBAT group B
INR	1.47	1.32	1.38
INR>1.5	24% to 36% *	18%	16%
Base deficit (mEq/L)	5.15	11.2	9.2
TEG G dynes/cm ²	4.9	7.3	7.5
Mortality	26%	12%	13%

* {MacLeod, 2003 #1415;Maegele, 2007 #905;Niles, 2008 #4410}

In addition, a slightly lower proportion of patients required transfusions (55% of group A, 61% of group B) compared to our anticipated proportion based on trauma registry data encompassing the period of January 2009-December 2011 (3 years) and excluding patients who died within 10 minutes of arriving at ED (64%).

Although we enrolled a cohort with less physiologic and coagulation derangement than anticipated, which decreased our statistical power to detect differences in the primary and secondary outcomes, we detected some promising trends, as follows:

[figure not shown]

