Mixed linear modeling with SAS Proc Mixed allows for incomplete data, thus all observed points will be used in the analysis. Missing data in temporal trends will be dealt with differently depending on the reason for missing. If MAR (loss to followup, withdrawn from study), multiple imputation methods will be used, as recommended by the Panel on Handling Missing Data in Clinical Trials. However, as described in previous sections, a major reason for missing data in these cases is early death, resulting in data MNAR, for which we will use the same approach to deal with the missing data as described for the secondary endpoints.

A similar analysis will be carried out for temporal trends in Proteomic Profile, Actin and Neutrophil Elastase inhibitors.

5. Blood components transfusion in the first 12 hours postinjury

a. Packed Red Blood Cells (RBC) volume

1. **Hypothesis:** The volume of RBC transfused in the first 12 hours postinjury will be larger among control patients compared to the experimental group patients.

b. Plasma volume

- **1. Hypothesis:** The volume of plasma transfused in the first 12 hours postinjury will be larger among control patients compared to the experimental group patients.
- 2. Statistical test for a.1 and b.2: These variables are usually non-normally distributed, thus the Wilcoxon non-parametric test will be used to compare the two groups and median/interquartile range will be used to express data central tendency and dispersion. If adjustment for covariates is needed, we will follow the procedure described for continuous, not normally distributed variables. Overall experiment error will be adjusted for the number of blood transfusion parameters being analyzed using the Bonferroni method.
- c. **Time to first RBC:** This is a variable of high importance for DOD, which leads to direct application in war theater trauma.

- **1. Hypothesis:** Time to the first RBC will be longer among patients in the experimental group compared to control patients.

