The contract with the Department of Defense is specific to the evaluation of the use of plasma in the field. As described above, the majority of potentially survivable injuries are due to hemorrhage. If administering plasma earlier in the field decreases hemorrhage from acute coagulopathy of trauma, injured members of the armed forces may have more time to reach a facility to be better stabilized and resuscitated. Although some institutions have adopted the principle of early plasma administration in the management of severe trauma and the acute coagulopathy of trauma, there are no prospective studies measuring the benefit and risks of administering plasma early.

Although this is a greater than minimal risk study, subjects are likely to receive direct benefit from this clinical trial from closer evaluation and testing of coagulation status. Based on the previous retrospective studies and preclinical studies described in the Section II.A. (Background) and Section III.A. (Preliminary studies) as well as our current understanding of administering plasma earlier and more frequently in the resuscitation of patients in severe hemorrhagic shock, patients receiving early plasma are likely to directly benefit from this study.

This study will be carried out in accordance with 21 CFR §50.24 Exception from Informed Consent for Emergency Research.

N. Description of Risks, Benefits and Justification

 Risk of blood transfusion: These risks apply to any patient that receives blood products regardless of group assignment. Both the standard and experimental groups are likely to receive blood products during the resuscitation period, but

the study group will receive at a minimum 2 units of AB plasma. In this study, all plasma used as an initial resuscitation fluid will be AB and hence universally infusible without the requirement for patient blood typing. This is the usual type of fresh frozen plasma used in acute trauma setting prior to obtaining type and cross

Table 3: Risk of Disease from Blood Product Transfusion				
Transmitted Blood Product Disease	US Transmission Risk/Unit Transfused			
Hepatitis A Virus (HAV)	1:8,300,000			
Hepatitis B Virus (HBV)	1:282,000			
Hepatitis C Virus (HCV)	1:1,149,000			
Human Immunodeficiency Virus (HIV-1, -2)	1:1,467,000			
Malaria	1:4,000,000			
Human T-cell lymphotrophicvirus (HTLV-I, -II)	1:2,990,000			

match (see appendix 9 for adult transfusion guidelines). Risks of blood

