- 6. Benefits: Utilizing AB plasma as the initial resuscitation fluid may increase the likelihood of survival, decrease multiple organ failure, and decrease the overall need for blood products, especially in the setting of activation of the massive transfusion protocol. Furthermore, implementation of this study may help patients in the future by giving important information about the treatment of acute blood loss and initial resuscitation in trauma. Benefits for patients in the control arm include intensive surveillance of the acute coagulopathy of trauma that may result in further appropriate medical treatment
- 7. Risk-Benefit analysis: Risks to the subject include reaction to risk of transmission of blood-borne pathogens, which is minimal, risk of reaction to blood transfusion, venipuncture, inadvertent release of PHI, or unforeseen happenings. Benefits include the potential to improve outcome in the critically injured with acute coagulopathy of trauma as well as decreased need for blood products. The risks of blood transfusion is small, but this specific trauma population that is severely injured and in hemorrhagic shock will likely receive transfusion of multiple blood products, including plasma, regardless of the type of initial resuscitation fluid. By transfusing AB plasma early as a resuscitation fluid, we may be able to slow down the ACoT, leading to a decreased number of transfused blood products. As stated above, transfusion of blood products in the first 12 hours is an independent risk factor of mortality.⁶³ Furthermore, using the same inclusion criteria as in the recent ROC hypertensive HTS trial,⁶⁷ mortality in this study is expected to exceed one in four. At the same time, massive pRBC infusion remains a major risk factor for MOF^{36, 38, 99} while plasma transfusion does not.
- 8. Adverse Events
 - a. The PRA team will be responsible for identifying and documenting adverse reactions. They will ask the principal investigator and the attending physician for the relatedness of the adverse reaction to study

and if they should be reported to the appropriate agencies. The DSMB as well as the RM will evaluate the relatedness of adverse reactions. All product related SAE's will be reported to the FDA within 15 calendar days.

b. The definitions of serious adverse events are from our MOF database and the Glue Grant study and in Table 4:

Table 4: Definitions of Serious Adverse Events			
Serious Adverse Events	Presentation and Treatment		

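### Aim 3 concerns overall blood product use, but no planned analysis measures the total, and an RBC fall alone cannot answer it

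*Combined protocol and SAP*

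**What the plan says.** Section I, aim 3, is to determine whether plasma-first resuscitation "decreases overall blood product transfusion and reduces the incidence of acute lung injury, multiple organ failure, and mortality". Section IV.N.6 (Benefits) repeats the idea, saying that plasma may "decrease the overall need for blood products, especially in the setting of activation of the massive transfusion protocol". The Military Significance paragraph before Section R notes that "Decreasing blood products transfusion in the initial postinjury period has implications for decreased need of precious blood products".

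The transfusion analyses are all in IV.G.5, among the exploratory analyses:
- RBC volume: "The volume of RBC transfused in the first 12 hours postinjury will be larger among control patients compared to the experimental group patients".
- Plasma volume: "The volume of plasma transfused in the first 12 hours postinjury will be larger among control patients compared to the experimental group patients".
- Time to first RBC, compared by Kaplan-Meier methods.

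The two volumes are compared by Wilcoxon test, with a Bonferroni adjustment for the number of transfusion parameters. IV.G.5 does not say whether the study plasma counts as plasma transfused.

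On the intervention, IV.N.1 says that "the study group will receive at a minimum 2 units of AB plasma" and puts the two units at 500 mL. On need, the November 2016 addendum in IV.E reports that "a slightly lower proportion of patients required transfusions (55% of group A, 61% of group B".

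**The concern.** The aim is about a sum and the analyses are about parts of it. That would matter little if the parts could be expected to move together. Here the design pushes one part up: the experimental arm is assigned two plasma units at the outset, including patients who would otherwise receive no product. RBC use and total use can then move in opposite directions.

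At stake is the wording of a conclusion. IV.I.1 lists statistically significant exploratory results among the measures for calling the therapy promising. The addendum also names the requirement for blood products among the outcomes that the enlarged sample should serve, without a calculation for it. A significant RBC fall could be written up as a lower need for blood products without anyone having computed the total. Section III.B describes AB plasma itself as limited in supply.

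**Working it through.** The documents give no sample size, power or effect size for any transfusion outcome, so there is no stated figure to reproduce.

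**1. Aim against analyses.** Aim 3 and IV.N.6 refer to overall product. IV.G.5 covers RBC amount, plasma amount and a time. A time is not an amount, no sum is defined, and platelets and cryoprecipitate are not analysed. No stated analysis answers the aim.

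**2. Break-even.** Inputs: 2 study units (IV.N.1), assuming both are given; share transfused 55% to 61% (IV.E addendum). Fall in other product needed per transfused patient = 2 / share transfused:
- 2 / 0.61 = 3.28 units
- 2 / 0.55 = 3.64 units

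**3. Size of that fall in relative terms.** The documents do not give RBC units per transfused patient (m), so a range is assumed. Take hospital plasma at half of RBC (the 1:2 starting ratio of the massive transfusion protocol, II.B) and 58% transfused (midpoint of 55% and 61%). Relative fall needed = 2 / (0.58 × 1.5 × m):

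| m | Fall needed to match the control total |
|---|---|
| 4 | 57% |
| 6 | 38% |
| 8 | 29% |
| 12 | 19% |

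**4. Can RBC fall significantly while the total rises?** Assumed scenario: plasma lowers the share transfused from 58% to 43%, with m unchanged. About 98 patients per arm (112 × 0.88 = 98.6). RBC tested by Wilcoxon at 0.05 / 2 = 0.025.

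Expected difference in total, experimental minus control = 2 − (0.58 − 0.43) × 1.5 × m = 2 − 0.225m. It is zero at m = 2 / 0.225 = 8.9.

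| m | Expected difference in total, units per patient | Simulated trials with a significant RBC fall and a higher total |
|---|---|---|
| 4 | +1.10 | about 36% |
| 6 | +0.65 | about 15% |
| 8 | +0.20 | about 5% |

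The last column moves with the assumed spread of RBC use between patients; a second simulation gave about 32%, 16% and 8%. The pattern is stable: divergence is plausible with light use and uncommon with heavy use.

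**5. Would a Wilcoxon test on the total settle it?** No. At m = 12 in the same scenario the expected total is 2 − 0.225 × 12 = −0.70, so mean use is lower with plasma. Yet the rank test called the total significantly higher with plasma in 36% of simulated trials (57% in the second simulation) and significantly lower in none. Two units given to everyone in one arm, set against about 42% zeros in the other, dominate the ranks.

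**The case against.** The strongest reply is that plasma volume is tested in its own right. If study units are counted, the excess is plain: in the scenario above, with RBC use varying widely between patients, that test goes against the experimental arm in at least 99% of simulated trials. A reader could then hardly mistake an RBC fall for an overall saving. This stands, but only under one reading of IV.G.5. If study units are left out, both component tests could favour plasma while the total rises. If they are counted, the two tests disagree and the plan has no rule for combining them.

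The scenario is also favourable to an RBC effect. The addendum's control-group inputs (12% mortality, INR 1.32, 18% with INR above 1.5, base deficit 11) match group A. Group B therefore appears to be the plasma group, with 61% transfused against 55%. At those shares the RBC test favours plasma in under 1% of simulated trials. The 58% to 43% contrast shows what can happen; it is not a forecast.

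It is fair too that the plan's account of harm centres on RBC. IV.N.6 and IV.N.7 nevertheless speak of blood products generally, and so does aim 3.

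Three stronger readings are tempting and unsupported:
- A reader might infer that the plan asserts a saving. The Military Significance sentence is conditional and IV.N.6 says only that plasma may have this effect; the mismatch lies between aim 3 and IV.G.5.
- A reader might take the chance of a significant RBC fall as the chance of a misleading conclusion. The relevant event is that fall together with a higher total, which is less frequent.
- A reader might assume that every experimental patient receives both units. IV.K allows for plasma thawed but not transfused and for transfusions stopped after a reaction, despite the minimum stated in IV.N.1.

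**Conclusion.** The gap is real: a stated aim has no analysis that answers it, and an RBC fall cannot stand in for one. The break-even of 2 units per randomised patient (3.3 to 3.6 per transfused patient) rests on both study units being given and on the interim shares transfused. The simulated 36%, 15% and 5% rest further on an assumed RBC use, an assumed plasma ratio and an assumed fall in the share transfused; above about 8.9 RBC units per transfused patient the expected total favours plasma. The documents do not show that total use would rise, only that the plan as written would not find out. The severity is minor: the analyses are exploratory and the primary endpoint is untouched.

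**What to change.** Add to IV.G.5 the total of all products in the first 12 hours per randomised patient: RBC, all plasma including study units actually given, platelets and cryoprecipitate. Report the difference in means with a bootstrap or permutation 95% confidence interval, using the same rule for early deaths as for RBC volume. Do not let a Wilcoxon test decide, for the reason in step 5.

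Tie aim 3 and the overall-need wording in IV.N.6 to this total, with the component results as support. If only RBC falls, the conclusion should be less RBC. Alternatively, reword aim 3, IV.N.6 and the Military Significance text to RBC use.

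No new data are needed, since IV.C.1.a already records blood products hourly. The cost is one more exploratory estimate and possibly a less favourable stated benefit. If the total is formally tested as a third volume parameter, the Bonferroni level goes from 0.05 / 2 = 0.025 to 0.05 / 3 = 0.0167.
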